c The Follow-up visit may be waived if the patient enrolls directly into another relugolix clinical study upon completion of the Week 104 visit.

d May be signed up to 30 days prior to the Week 24/Baseline visit or during the Week 24/Baseline visit. Enrollment in MVT-601-3103 is defined by administration of the first dose of MVT-601-3103 study drug.

- e Record all prescription and nonprescription drug and supplements taken from the Week 24/Baseline visit through the Safety Follow-Up Period. Concomitant medications with start date prior to the first dose of study drug for MVT-601-3103 should be reported as concomitant medications in the parent study (MVT-601-3101 or MVT-601-3102). If concomitant medication is ongoing at the time of the first dose of study drug for MVT-601-3103, please see the Case Report Form Completion Guidelines for instructions for recording the follow-up status.
- f Concomitant medications are recorded both for the parent study and for MVT-601-3103 at the Week 24/Baseline visit. (See footnote e for further details).
- g This is a parent study (MVT-601-3101 or MVT-601-3102) Week 24 procedure that serves as the Week 24/Baseline procedure for MVT-601-3103 and is covered under the informed consent for the parent study.
- h The indicated procedure may be performed at the Unscheduled visit based on the purpose of the visit (eg, follow-up for an adverse event or abnormal laboratory test).
- i The Week 52 and Week 104 physical examinations will include a breast examination.
- j See parent study protocols (MVT-601-3101 or MVT-601-3102) for instructions on testing visual acuity.
- k The examination may include a gynecologic examination, if indicated based on signs and symptoms.
- l The 12-lead ECGs will be submitted for central reading.
- m Clinical chemistries will be collected at each visit. A complete blood count will be collected at Week 24/Baseline, Week 28, Week 36, Week 52, Week 65, Week 78, Week 91, and Week 104/Early Termination. At the Week 24/Baseline visit, Week 52 visit, and Week 104/Early Termination visit, additional tests will include the following: fasting (at least 8 hours) glucose, lipid profile, and hemoglobin A1c.
- n Samples should be obtained in a fasted state (at least 8 hours). Water is allowed during the fasting period.

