Patients will continue recording data in their eDiary daily and taking protocol-specified analgesics as needed until Week 52. After Week 52, the eDiary will be collected on the following schedule: Week 57 to the Week 65 visit, Week 71 to the Week 78 visit, Week 85 to the Week 91 visit, and Week 98 to the Week 104 visit. Following the Week 24/Baseline visit, on-treatment study visits will occur at Weeks 28, 32, 36, 40, 44, 48, 52, 65, 78, 91, and 104. Sites will monitor diary completion using the Trial Manager web portal throughout the study.

A telephone call will be performed at Weeks 57, 71, 85 and 98. The following activities should be completed: a concomitant medication review, an evaluation of adverse events, a review of study medication compliance, a reminder of compliance with non-hormonal contraception requirements and the need to call the investigator if pregnancy is suspected, and a reminder to the patient to start recording in the eDiary daily.

Accountability for study drug will be performed at each visit. Instructions for analgesic medication usage will be reinforced at each visit.

Questionnaires are administered on the electronic tablet and on paper at each visit. These procedures should occur before any other types of study procedures are performed. When both electronic tablet and paper questionnaires are required at a visit, the electronic questionnaires should be done first. The order in which the electronic tablet and paper questionnaires should be administered are as follows:

- Electronic tablet questionnaires (in the order they appear in the tablet)
- Paper questionnaires
  - PGA for function
  - EHP Work Domain [Week24/Baseline, Week 52, Week 78, and Week 104 only]

Patients will bring their eDiary, analgesic medications, and study drug to each visit. The site must document the start and stop dates of the patient's menses.

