An endometrial biopsy will have been performed at the parent study Week 24 visit for all patients who participated in MVT-601-3101 (see MVT-601-3101 protocol for details). An endometrial biopsy is required at Week 52 and the Early Termination visit for all patients. This procedure is not required at the Early Termination visit in patients whose last dose of study drug was taken during Week 32 or earlier or within four weeks after completion of the Week 52 endometrial biopsy. However, the procedure may be done if it will aid in the evaluation of an ongoing adverse event. An endometrial biopsy at Week 104 is recommended for all patients who complete the open-label extension; however, patients will have the option to opt out. Safety monitoring for this study includes physical examination, clinical laboratory tests, pregnancy tests, and adverse event collection at each visit. Clinical chemistries will be collected at each visit. A complete blood count will be collected at Week 24/Baseline, Week 28, Week 36, Week 52, Week 65, Week 78, Week 91, and Week 104/Early Termination. At the Week 24/Baseline

visit, Week 52 visit, and Week 104/Early Termination visit, additional tests include fasting (at least 8 hours, other than water) glucose, lipid profile, and hemoglobin A1c.

Electrocardiograms will be performed at the Week 24/Baseline, Week 52, and Week 104/Early Termination visits.

A mammogram will be performed at Week 52 or at Week 104/Early Termination for women who are or become  $\geq 40$  years old during the study (see Section 6.5.2.9).

Bone densitometry will occur at the Week 24/Baseline, Week 36, Week 52, and Week 104/Early Termination visits. Follow-up of bone densitometry findings will proceed according to the rules described in Section 6.5.2.6.

Bone densitometry and ECGs will be submitted for central reading.

Study drug compliance will be reviewed at each visit. Fasting (other than water) for at least 8 hours is required prior to blood sampling on Week 24/Baseline and Week 52/Early Termination visits and for 1 hour after administration of the study drug in the clinic. Laboratory requisitions must indicate whether or not the patient was not fasted for their chemistry and lipid testing.

Refer to the Schedule of Activities (see Section 1.1) for information about study procedures during the Open-Label Treatment Period.

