
Phospholipidosis
 
Data from nonclinical studies in rats and monkeys showed histopathological changes consistent with PLD. PLD by itself is not adverse. No clinical evidence of relugolix-related PLD-associated toxicity has been observed nor was there a clinically meaningful increase in a biomarker of PLD assessed in phase 2 clinical studies.
	
Patients with significant underlying medical conditions are excluded.
	
Routine safety monitoring including laboratory assessments, ECGs, and assessment of adverse events, including any ophthalmologic adverse events, will be monitored during this study.

Metabolic Changes
 
Metabolic changes (insulin resistance, dyslipidemia, and increased weight) with increased risk of diabetes are a potential risk of the hypoestrogenic state induced by relugolix.
	
Exclusion criteria for current medical history of cardiovascular disease in the parent studies.
	
Fasting lipids and glucose will be monitored during the study.

Reproductive Toxicity
	
Premenopausal compliance with specified acceptable non-hormonal contraception; exclusion of pregnant and lactating women.
	
Pregnancy testing at each study visit; immediate withdrawal for pregnancy.

Potential Risk of Clinical Significance	Mitigation Strategy	
	Impact on Eligibility	Monitoring and Withdrawal Criteria

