## 9.5. Safety Analyses

Safety assessments will include treatment-emergent adverse events, vital signs and weight, physical examinations, clinical laboratory tests, 12-lead ECG, bone mineral density with DXA, mammograms (for patients required to have this procedure, see Section 6.5.2.9), and endometrial biopsy. Safety summaries by treatment group will be performed using treatment groups defined based on the actual randomized treatment received in the parent study.

The treatment-emergent period will be defined as the period of time from the first dose date and time of randomized study drug in the parent study through 30 days after the last dose of study drug, or the date of initiation of another investigational agent or hormonal therapy affecting the hypothalamic-pituitary-gonadal axis or surgical intervention for endometriosis, whichever occurs first. Safety will be assessed through summaries of adverse events, the frequency of treatment discontinuations due to adverse events, laboratory evaluations, and bone densitometry results.

The severity of all adverse events is to be evaluated by the investigator based on the National Cancer Institute CTCAE. All adverse events will be coded to preferred term, high level term, and system organ class using MedDRA 20.0 or higher. The incidence of adverse events will be presented by MedDRA system organ class and preferred term, relationship to study drug treatment, and severity. A patient reporting the same adverse event more than once is counted

once, and at the maximum severity or strongest relationship to study drug treatment when calculating incidence.

Laboratory data consist of chemistry, hematology, and hormonal tests. Only data collected by the central laboratory will be used to do the analyses. The National Cancer Institute CTCAE will be used to categorize toxicity grade for the laboratory parameters. Shift tables will be provided for each gradable parameter to summarize baseline toxicity grade versus post-baseline toxicity grade. For laboratory parameters that are not gradable by the CTCAE, a shift table based upon the normal range (low, normal, and high) will be provided for each parameter to summarize the parent study Baseline versus post-baseline results. All data will be listed and summarized by visit. The change from parent study Baseline to each post-baseline study visit will be presented by parent study treatment group for each laboratory test.

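### Section 6.2 contradicts itself and the Schedule of Activities on whether Week 104 blood samples must be fasted; a minor second point is that Section 9.5 makes no use of recorded fasting status for glucose

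*Protocol*

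**What the plan says.** On fasting, the protocol speaks in four places.

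- Section 6.2, near its end: "Fasting (other than water) for at least 8 hours is required prior to blood sampling on Week 24/Baseline and Week 52/Early Termination visits". Week 104 is not named.
- Section 6.2, in the earlier paragraph on safety monitoring: fasting glucose, lipid profile and hemoglobin A1c are extra tests at Week 24/Baseline, Week 52 and Week 104/Early Termination.
- Schedule of Activities, footnote m, for the same three visits: "additional tests will include the following: fasting (at least 8 hours) glucose, lipid profile, and hemoglobin A1c".
- Schedule of Activities, footnote n, attached in the clinical laboratory row to those three visits only. It begins "Samples should be obtained in a fasted state (at least 8 hours" and goes on to allow water.

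On collection, footnote m also says "Clinical chemistries will be collected at each visit", and Table 6-1 lists glucose under Chemistry. Section 6.2 adds that "Laboratory requisitions must indicate whether or not the patient was not fasted for their chemistry and lipid testing".

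On purpose, Table 7-2 names insulin resistance, dyslipidemia and diabetes as potential risks and gives the monitoring as "Fasting lipids and glucose will be monitored during the study".

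On analysis, Section 9.5 grades laboratory parameters by CTCAE, tabulates shifts in grade for each gradable parameter, and states "The change from parent study Baseline to each post-baseline study visit will be presented by parent study treatment group for each laboratory test". It sets no condition on fasting.

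**The concern.** The Section 6.2 sentence is an instruction about how blood is to be drawn. A site that takes it literally has no reason to ask a completing patient to fast before Week 104. The glucose and lipids drawn there would then be unfasted at the final analysis point, while the table of risks assumes they are fasted. An analysis can filter out samples flagged as unfasted, but it cannot supply the fasted value that was never taken.

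The second point concerns the analysis. If glucose is measured with the chemistry panel at every visit, most visits have no fasting requirement, yet Section 9.5 treats every visit's value alike for grading, shifts and change from Baseline. Rows at those visits may mix fasted and fed samples. In a single-arm study no concurrent control group shows how much of a change is due to meals.

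**Working it through.** **Step 1: set the fasting statements side by side.**

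| Place in the protocol | Week 24 | Week 52 | Week 104 | Early Termination |
|---|---|---|---|---|
| Schedule of Activities, laboratory row with footnote n | fasted | fasted | fasted | fasted |
| Footnote m | fasted | fasted | fasted | fasted |
| Section 6.2, earlier sentence | fasted | fasted | fasted | fasted |
| Section 6.2, later sentence | fasted | fasted | not named | fasted |

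The conflict is confined to one cell: patients who complete the study and attend Week 104. Early Termination is covered everywhere, although the later sentence pairs it with Week 52 and the Schedule pairs it with Week 104.

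**Step 2: count what depends on that cell.** Section 6.2 says that "on-treatment study visits will occur at Weeks 28, 32, 36, 40, 44, 48, 52, 65, 78, 91, and 104", which is 11 visits.

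- Fasting required under footnotes m and n: Weeks 52 and 104, so 2 of 11.
- Fasting required under the later Section 6.2 sentence: Week 52 only, so 1 of 11.
- After Week 52 there are 4 visits (65, 78, 91, 104). Footnotes m and n give 1 fasted visit among them. The later sentence gives 0 for a patient who completes.

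Read literally, then, the later sentence leaves completers with no required fasted glucose or lipid sample between Week 52 and the end of treatment. The lipid profile is scheduled only at Weeks 24, 52 and 104/Early Termination, so no other lipid sample can stand in.

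**Step 3: the second point.** Assume that glucose is run at each visit as part of chemistry.

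- Visits after Week 24 with no fasting requirement: 11 − 2 = 9, and 9/11 = 81.8%.
- Up to the Week 52 analysis: 7 visits, 1 with a required fast, so 6/7 = 85.7% without.

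**Step 4: which rows could be mixed.** Section 9.5 summarizes data by visit, and the synopsis describes laboratory shifts from parent Baseline to each later visit. The nine rows without a required fast may be mixed. The Week 52 and Week 104 rows contain only fasted samples if patients fast as footnote n requires, so restricting the tables to fasted samples would leave those two rows unchanged.

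The documents give no glucose mean, standard deviation or meal effect. They also do not give the share of patients who would arrive unfasted, or the fasting rule at parent Baseline. I therefore put no figure on the size of any resulting shift.

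**The case against.** On the first point, the best reply is that this is a slip of wording. Three statements agree, one does not, and sites usually work from the Schedule. That limits how often the error would be acted on, and the documents give no way to estimate how often. It does not remove the contradiction. It could also be said that Section 5.4 has patients take study drug in the clinic at Week 104 in a fasted state. That fast allows tea and coffee and can be met two hours after a meal, so it is not the 8-hour fast. Section 6.5.1.1 moreover says that no dose is given at Week 104.

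On the second point, three replies carry weight. Handling of fasted and unfasted values is detail that the SAP may settle, and the SAP is not shown. Glucose at every visit is the natural reading of footnote m and Table 6-1, but it is an inference: the Chemistry column also lists hemoglobin A1c, which is not drawn at every visit. And a visit without a required fast is not a visit with a fed sample. These make the point minor.

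A reader might go further and infer that unfasted samples dominate the readout of diabetes risk. The documents do not support that. Tables are by visit, so Weeks 52 and 104, the two analysis time points, stand apart. Only a table of each patient's worst value over all visits would be dominated in that way. Section 9.5 does not say which post-baseline grade its shift tables use, but the synopsis points to shifts at each visit.

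A reader might also infer that a drug effect and a meal effect cannot be told apart. That is not so either: fasting status is recorded on the requisition, and hemoglobin A1c, which does not depend on fasting at the draw, is measured at Weeks 24, 52 and 104.

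**Conclusion.** The contradiction in Section 6.2 is real and worth correcting. It affects one visit, Week 104 in completers, but that visit is one of only two fasted time points after Week 24 and the only scheduled one after Week 52. The consequence depends on sites following the later Section 6.2 sentence, which cannot be judged from the documents.

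The second point is minor. It rests on glucose being run at every visit. Given that, 9 of 11 by-visit glucose rows (82%) may mix fasted and fed samples. It does not reach the Week 52 and Week 104 rows if patients fast as required, and it does not extend to lipids, which are scheduled only at the fasting visits.

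**What to change.** Reconcile the later fasting sentence in Section 6.2 with footnotes m and n, so that every place in the protocol names the same fasting visits. This costs one line of wording and a note to sites.

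In Section 9.5, state that glucose grades, shift tables and change from Baseline use samples flagged as fasted on the requisition, and that unfasted glucose is tabulated separately. If the SAP already says this, no further change is needed. The flag is already collected, so the cost is a filter in the programming; the downside is fewer glucose values in the graded tables. The filter does not replace the first change, because it cannot recover a Week 104 sample drawn without a fast.

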## **9.6. Pharmacodynamics Analyses**

The change from the parent study Baseline to Week 52 and to Week 104 in predose concentrations of serum estradiol will be summarized. Percentage of patients with concentrations of serum estradiol levels < 10 pg/mL and < 20 pg/mL will be provided.

## **9.7. Exploratory Analyses**

Descriptive summaries by treatment group will be provided for the following exploratory endpoints. Details on the endpoint analyses including deviations, handling of missing data, and statistical methods will be provided in the SAP. The following exploratory endpoints will be assessed at Week 52 and Week 104:

- Change from Baseline in the EHP-30 scale total score;
- Change from Baseline in the EHP Work Domain score;
- Change from parent study Baseline in the EQ-5D-5L.

## **9.8. Interim Analyses**

An interim analysis will be conducted at Week 52 in which all efficacy and safety endpoints will be assessed as described above. A clinical study report will be generated based on these data to support submission of one-year data.

## **9.9. Steering Committee**

The study will be overseen by a Steering Committee consisting of experts in the field of women's health and staff members of Myovant Sciences GmbH. The Steering Committee will participate in the design, conduct, analyses, and publication of the study.

---

## **10. RESPONSIBILITIES**

### **10.1. Investigator Responsibilities**

#### **10.1.1. Good Clinical Practice**

The investigator will ensure that this study is conducted in accordance with the principles of the “Declaration of Helsinki” (as amended in Edinburgh, Tokyo, Venice, Hong Kong, and South Africa), International Council on Harmonisation (ICH) guidelines, or with the laws and regulations of the country in which the research is conducted, whichever affords the greater protection to the study participant. For studies conducted under a US investigational new drug application, the investigator will ensure that the basic principles of “Good Clinical Practice,” as outlined in 21 Code of Federal Regulations (CFR 312), subpart D, “Responsibilities of Sponsors and Investigators,” 21 CFR, part 50, 1998, and 21 CFR, part 56, 1998, are adhered to. These standards are consistent with the requirements of the European Community Directive 2001/20/EC.

Since this is a “covered” clinical study, the investigator will ensure that 21 CFR, Part 54, 1998, is adhered to; a “covered” clinical study is any “study of a drug or device in humans submitted in a marketing application or reclassification petition subject to this part that the applicant or FDA relies on to establish that the product is effective (including studies that show equivalence to an effective product) or that make a significant contribution to the demonstration of safety.” This requires that investigators and all sub-investigators must provide documentation of their financial interest or arrangements with the sponsor, or proprietary interests in the drug being studied. This documentation must be provided before participation of the investigator and any sub-investigator. The investigator and sub-investigator agree to notify the sponsor of any change in reportable interests during the study and for 1 year following completion of the study.

#### **10.1.2. Institutional Review Board/Independent Ethics Committee Approval**

This protocol and any accompanying material to be provided to the patient (such as advertisements, patient information sheets, or descriptions of the study used to obtain informed consent) will be submitted by the investigator to an IRB or IEC. Approval from the IRB or IEC must be obtained before starting the study and should be documented in a letter to the investigator specifying the protocol number, protocol version, protocol date, documents reviewed, and date on which the committee met and granted the approval.

Any modifications made to the protocol after receipt of IRB or IEC approval must also be submitted to the IRB or IEC for approval before implementation.

#### **10.1.3. Informed Consent**

The investigator is responsible for obtaining written informed consent from each individual participating in this study after adequate explanation of the aims, methods, objectives, and potential hazards of the study and before undertaking any study-related procedures. The investigator must utilize an IRB- or IEC-approved informed consent form for documenting written informed consent that contains all elements required by national, state, local, and institutional regulations or requirements. Each informed consent form will be appropriately

signed and dated by the patient or the patient's legally authorized representative and the person obtaining consent.

#### **10.1.4. Confidentiality**

The investigator must assure that patients' anonymity will be strictly maintained and that their identities are protected from unauthorized parties. Only patient number, date of birth, and an identification code (ie, not names) should be recorded on any form or biological sample submitted to the sponsor, IRB or IEC, or laboratory. The investigator must keep a screening log showing codes, names, and addresses for all patients screened and for all patients enrolled in the study.

The investigator agrees that all information received from the sponsor, including but not limited to the Investigator Brochure, protocol, eCRFs and other study forms, the investigational drug, and any other study information, remain the sole and exclusive property of the sponsor during the conduct of the study and thereafter. This information is not to be disclosed to any third party (except employees or agents directly involved in the conduct of the study or as required by law) without prior written consent from the sponsor. The investigator further agrees to take all reasonable precautions to prevent the disclosure by any employee or agent of the study site to any third party or otherwise into the public domain.

